Occurrence of menses will be captured on the memory aid. *L. crispatus* CTV-05 concentration and time since last day of the last menstrual period will be presented graphically for each visit, treatment group, and analysis population in [Figure 21](#), [Figure 22](#), [Figure 23](#), and [Figure 24](#). A smoothing spline regression model will be fit with treatment group as an independent variable. The fitted curves with 95% confidence bands will be included in the figures. Model fit and inference of the parameters will be commented on in the final report but not included in a table.

L. crispatus colonization will be also be presented by occurrence of menses after the last dose taken in [Table 50](#), [Table 51](#), [Table 52](#), and [Table 53](#). Subjects will be categorized as menstruating after their last dose taken before the visit presented, or not menstruating after the last dose taken before the specified visit. If there are less than three subjects in either treatment group who had menses since their last dose for a specified visit, that visit will be excluded from the table. Box plots of *L. crispatus* CTV-05 concentration by occurrence of menses are provided for each treatment group, visit, and analysis population in [Figure 25](#), [Figure 26](#), [Figure 27](#), and [Figure 28](#).

For all by-visit summaries, the proportions of subjects with colonization at a visit is defined as follows: the numerator is the number of subjects who experience recurrence at the specified visit and the denominator of the proportion of subjects with BV recurrence is the number of subjects in the analysis population and subgroup who returned for that visit.

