1: 95% CI= 95% Wilson confidence interval

2: Difference in 95% CI=asymptotic 95% CI from a Chi-Square test

3: p-value calculated from the Chi Square Test.

Tables with similar format:

Table 22: *L. crispatus* Colonization at Visit 7 (Week 24) by Analysis Population and Treatment Group

Table 23: *L. crispatus* Colonization by Study Day and Treatment Group – ITT Population

Study Day (Week)	Treatment Group	Number of Subjects with Colonization n	Number of Subjects N	Proportion of Subjects with Colonization	Colonization 95% CI ¹	Odds of Colonization in LACTIN-V Group Compared to Placebo Group	Odds of Colonization in LACTIN-V Group Compared to Placebo Group 95% CI ²	p-value ³
Day 1	LACTIN-V	x	x	0.xx	0.xx, 0.xx	x.xx	x.xx, x.xx	0.xxx
	Placebo	x	x	0.xx	0.xx, 0.xx	--	--	
	All Subjects	x	x	0.xx	0.xx, 0.xx	--	--	
Day 28 (Week 4)	LACTIN-V	x	x	0.xx	0.xx, 0.xx	x.xx	x.xx, x.xx	0.xxx
	Placebo	x	x	0.xx	0.xx, 0.xx	--	--	
	All Subjects	x	x	0.xx	0.xx, 0.xx	--	--	
Day 56 (Week 8)	LACTIN-V	x	x	0.xx	0.xx, 0.xx	x.xx	x.xx, x.xx	0.xxx
	Placebo	x	x	0.xx	0.xx, 0.xx	--	--	
	All Subjects	x	x	0.xx	0.xx, 0.xx	--	--	
Day 84 (Week 12)	LACTIN-V	x	x	0.xx	0.xx, 0.xx	x.xx	x.xx, x.xx	0.xxx
	Placebo	x	x	0.xx	0.xx, 0.xx	--	--	
	All Subjects	x	x	0.xx	0.xx, 0.xx	--	--	
Day 168 (Week 24)	LACTIN-V	x	x	0.xx	0.xx, 0.xx	x.xx	x.xx, x.xx	0.xxx
	Placebo	x	x	0.xx	0.xx, 0.xx	--	--	
	All Subjects	x	x	0.xx	0.xx, 0.xx	--	--	

Note: The denominator for rate estimates is based on the number of subjects in the respective treatment group and analysis population with colonization data available at the specified visit.

1: 95% CI= 95% Wilson confidence interval

2: Difference in 95% CI=asymptotic 95% CI from a Chi-Square test

3: p-value calculated from the Chi Square Test.

Tables with similar format:

Table 24: *L. crispatus* Colonization by Study Day and Treatment Group – mITT Population

Table 25: *L. crispatus* Colonization by Study Day and Treatment Group – CC Population

Table 26: *L. crispatus* Colonization by Study Day and Treatment Group – PP Population

Table 27: *L. crispatus* CTV-05 Concentration by Study Day and Treatment Group – ITT Population

Study Day (Week)	Treatment Group	Number of Subjects ¹	Mean (SD)	Median	Range
Day 1	LACTIN-V	x	x.xx (x.xx)	x.xx	x.xx, x.xx
	Placebo	x	x.xx (x.xx)	x.xx	x.xx, x.xx
	All Subjects	x	x.xx (x.xx)	x.xx	x.xx, x.xx
Day 28 (Week 4)	LACTIN-V	x	x.xx (x.xx)	x.xx	x.xx, x.xx
	Placebo	x	x.xx (x.xx)	x.xx	x.xx, x.xx
	All Subjects	x	x.xx (x.xx)	x.xx	x.xx, x.xx

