	All Subjects	1 st Quartile	x	x	0.xx	0.xx, 0.xx
		2 nd Quartile	x	x	0.xx	0.xx, 0.xx
		3 rd Quartile	x	x	0.xx	0.xx, 0.xx

Study Day (Week)	Treatment Group	Number of Condom-less Sex Acts Since the Previous Visit	Number of Subjects with Colonization n	Number of Subjects N	Proportion of Subjects with Colonization	Colonization 95% CI ¹
		4 th Quartile	x	x	0.xx	0.xx, 0.xx
Day 84 (Week 12)	LACTIN-V	1 st Quartile	x	x	0.xx	0.xx, 0.xx
		2 nd Quartile	x	x	0.xx	0.xx, 0.xx
		3 rd Quartile	x	x	0.xx	0.xx, 0.xx
		4 th Quartile	x	x	0.xx	0.xx, 0.xx
	Placebo	1 st Quartile	x	x	0.xx	0.xx, 0.xx
		2 nd Quartile	x	x	0.xx	0.xx, 0.xx
		3 rd Quartile	x	x	0.xx	0.xx, 0.xx
		4 th Quartile	x	x	0.xx	0.xx, 0.xx
	All Subjects	1 st Quartile	x	x	0.xx	0.xx, 0.xx
		2 nd Quartile	x	x	0.xx	0.xx, 0.xx
		3 rd Quartile	x	x	0.xx	0.xx, 0.xx
		4 th Quartile	x	x	0.xx	0.xx, 0.xx
Day 168 (Week 24)	LACTIN-V	1 st Quartile	x	x	0.xx	0.xx, 0.xx
		2 nd Quartile	x	x	0.xx	0.xx, 0.xx
		3 rd Quartile	x	x	0.xx	0.xx, 0.xx
		4 th Quartile	x	x	0.xx	0.xx, 0.xx
	Placebo	1 st Quartile	x	x	0.xx	0.xx, 0.xx
		2 nd Quartile	x	x	0.xx	0.xx, 0.xx
		3 rd Quartile	x	x	0.xx	0.xx, 0.xx
		4 th Quartile	x	x	0.xx	0.xx, 0.xx
	All Subjects	1 st Quartile	x	x	0.xx	0.xx, 0.xx
		2 nd Quartile	x	x	0.xx	0.xx, 0.xx
		3 rd Quartile	x	x	0.xx	0.xx, 0.xx
		4 th Quartile	x	x	0.xx	0.xx, 0.xx

Note: The denominator for rate estimates is based on the number of subjects in the respective treatment group and analysis population with colonization and condomless sex act data available at the specified visit.

*Number of condom-less sexual intercourse acts in the last 30 days

1: 95% CI= 95% Wilson confidence interval

Implementation note: Quartiles will be filled in with the actual ranges

Tables with similar format:

Table 32: *L. crispatus* Colonization by Study Day, Treatment Group, and Number of Condom-less Sexual Intercourse Acts – mITT

Table 33: *L. crispatus* Colonization by Study Day, Treatment Group, and Number of Condom-less Sexual Intercourse Acts – CC Population

Table 34: *L. crispatus* Colonization by Study Day, Treatment Group, and Number of Condom-less Sexual Intercourse Acts – PP Population

Table 35: *L. crispatus* Colonization by Study Day, Treatment Group, and Number of Partners – ITT Population

Study Day (Week)	Treatment Group	Number of Partners Since the Previous Visit	Number of Subjects with Colonization n	Number of Subjects N	Proportion of Subjects with Colonization	Colonization 95% CI ¹

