Table 48: Days Since Last Day of Last Menstrual Period by Study Day, Treatment Group, and *L. crispatus* Colonization Status – CC Population

Table 49: Days Since Last Day of Last Menstrual Period by Study Day, Treatment Group, and *L. crispatus* Colonization Status – PP Population

Table 50: *L. crispatus* Colonization by Study Day, Treatment Group, and Occurrence of Menses After Last Dose Taken – ITT Population

Study Day (Week)	Treatment Group	Occurrence of Menses	Number of Subjects with Colonization n	Number of Subjects N	Proportion of Subjects with Colonization	Colonization 95% CI ¹	Odds of Colonization in Subjects with Menses Compared to Subjects with No Menses	Odds of Colonization in Subjects with Menses Compared to Subjects with No Menses 95% CI ²
Day 28 (Week 4)	LACTIN-V	Menses since last dose	x	x	0.xx	0.xx, 0.xx	x.xx	x.xx, x.xx
		No menses since last dose	x	x	0.xx	0.xx, 0.xx	--	--
	Placebo	Menses since last dose	x	x	0.xx	0.xx, 0.xx	x.xx	x.xx, x.xx
		No menses since last dose	x	x	0.xx	0.xx, 0.xx	--	--
Day 56 (Week 8)	LACTIN-V	Menses since last dose	x	x	0.xx	0.xx, 0.xx	x.xx	x.xx, x.xx
		No menses since last dose	x	x	0.xx	0.xx, 0.xx	--	--
	Placebo	Menses since last dose	x	x	0.xx	0.xx, 0.xx	x.xx	x.xx, x.xx
		No menses since last dose	x	x	0.xx	0.xx, 0.xx	--	--
Day 84 (Week 12)	LACTIN-V	Menses since last dose	x	x	0.xx	0.xx, 0.xx	x.xx	x.xx, x.xx
		No menses since last dose	x	x	0.xx	0.xx, 0.xx	--	--
	Placebo	Menses since last dose	x	x	0.xx	0.xx, 0.xx	x.xx	x.xx, x.xx
		No menses since last dose	x	x	0.xx	0.xx, 0.xx	--	--
Day 168 (Week 24)	LACTIN-V	Menses since last dose	x	x	0.xx	0.xx, 0.xx	x.xx	x.xx, x.xx
		No menses since last dose	x	x	0.xx	0.xx, 0.xx	--	--
	Placebo	Menses since last dose	x	x	0.xx	0.xx, 0.xx	x.xx	x.xx, x.xx
		No menses since last dose	x	x	0.xx	0.xx, 0.xx	--	--

Note: The denominator for rate estimates is based on the number of subjects in the respective treatment group and analysis population with colonization and menses data available at the specified visit.

1: 95% CI= 95% Wilson confidence interval

2: Difference in 95% CI=asymptotic 95% CI from a Chi-Square test

Tables with similar format:

Table 51: *L. crispatus* Colonization by Study Day, Treatment Group, and Occurrence of Menses After Last Dose Taken – mITT Population

Table 52: *L. crispatus* Colonization by Study Day, Treatment Group, and Occurrence of Menses After Last Dose Taken – CC Population

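### SAP 8.2 defines the by-visit colonization proportion with a BV-recurrence numerator and a denominator that the SAP's own table notes contradict

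*SAP*

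**What the plan says.** After describing the colonization tables, SAP 8.2 gives one definition for all by-visit summaries. It begins "the proportions of subjects with colonization at a visit is defined as follows". It then states that "the numerator is the number of subjects who experience recurrence at the specified visit" and that "the denominator of the proportion of subjects with BV recurrence is the number of subjects" in the population and subgroup attending, in full "the number of subjects in the analysis population and subgroup who returned for that visit".

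Other parts of the SAP bear on the same quantity:

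- **3.3.3** defines successful colonization from qPCR: CTV-05 and *L. crispatus* must both be above their detection limits. A result below the limit or indeterminate counts as not colonized. BV status plays no part.
- **Appendix 1, Table 23 note** (Tables 24 to 26 share the format) uses subjects in the arm and "analysis population with colonization data available at the specified visit".
- **Table 31 note** (condom-less intercourse) uses subjects "with colonization and condomless sex act data available at the specified visit". **Table 50 note** (menses) uses subjects "with colonization and menses data available at the specified visit". The notes to Tables 35 (partners) and 43 (compliance) follow the same pattern.
- **Notes to Tables 77 and 81** (by Amsel and Nugent status) use everyone in the arm and population, although 8.3 says that these tables follow the analyses for Tables 23 to 26.
- **6.5** says that missing data are not imputed in by-study-day displays of colonization.

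**The concern.** A rule announced as the definition of a colonization proportion counts a different event and labels its own denominator as that of BV recurrence. Its denominator also disagrees with the table notes. A woman who attends but has no qPCR result stays in the denominator under the text and drops out under the notes. Under the text she is in effect counted as not colonized, which is imputation by another route and conflicts with 6.5.

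The rule governs more than descriptive displays. SAP secondary outcomes 1 and 5 (numbered 1 and 2 in the protocol) include colonization by menses and intercourse, and those breakdowns are planned only as by-visit tables. Tables 23 to 26 also carry odds ratios and chi-square tests. If the denominator is left open, it could be chosen after results are seen.

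**Working it through.** The documents state no figure for the by-visit colonization proportion, so there is none to reproduce. The check is a comparison of texts followed by an illustration of size.

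**Numerator.** The sentence nearly repeats the by-visit BV recurrence definition given earlier in 8.2. A similar slip occurs in the time-to-colonization paragraph, which promises Kaplan-Meier estimates of time to BV recurrence. SAP Section 13 does not correct either. The shells for Tables 23, 31, 35, 43 and 50 head the count column as subjects with colonization. The intended numerator is therefore clear, and the word in the text is wrong.

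**Denominator.** Three versions stand side by side:

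| Place | Denominator |
|---|---|
| 8.2 text | returned for the visit |
| Notes to Tables 23, 31, 35, 43, 50 | colonization (and subgroup) data available at the visit |
| Notes to Tables 77, 81 | all subjects in arm and population |

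Only the second agrees with the no-imputation rule in 6.5. The same mismatch exists for by-visit BV recurrence: the 8.2 text uses subjects who returned, and the Table 13 note uses subjects with BV diagnosis data.

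**Size of the denominator effect.** Let c be the proportion colonized among women with a result, and m the share of attendees with no result. Dividing by attendees gives c × (1 − m), so the shift is c × m. For c, take the Phase II-a ITT figure of 61% (95% CI 36% to 83%; protocol 2.1). For m, no rate is given, so 0%, 5% and 10% are assumed.

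| c | m = 0% | m = 5% | m = 10% |
|---|---|---|---|
| 36% | 36% | 0.36 × 0.95 = 34% | 0.36 × 0.90 = 32% |
| 61% | 61% | 0.61 × 0.95 = 58% | 0.61 × 0.90 = 55% |
| 83% | 83% | 0.83 × 0.95 = 79% | 0.83 × 0.90 = 75% |

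In whole women: the LACTIN-V arm is 228 × 2/3 = 152, and 152 × 0.90 = 137 return if the plan's 10% drop-out is borrowed. With 5% of results absent, 130 have data and 79 are colonized: 79/130 = 61%, but 79/137 = 58%. With 10% absent, 123 have data and 75 are colonized: 75/123 = 61%, but 75/137 = 55%.

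**The case against.** The strongest reply is that this is a copying slip that no competent programmer would carry out, since a column headed as subjects with colonization could not sensibly be filled with BV recurrences. That stands for the numerator.

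On the denominator, the reply is that the gap is narrow. 3.3.3 classes an indeterminate result as not colonized by definition, so only a wholly absent result separates the two denominators. The protocol schedules a qPCR swab at every follow-up clinic visit. For the main colonization analyses, 6.5 itself counts missing or unevaluable results as unsuccessful, so the downward direction is one that the SAP accepts there. This limits the likely size, but it does not remove the conflict: 6.5 sets a different rule for by-study-day displays, and the text and the notes cannot both be followed.

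A reader might infer that the secondary colonization endpoint as a whole is wrong. The documents do not support this. Table 21 (any time through Visit 4) and Table 22 (Visit 7) have their own denominator, everyone in the arm and population, and 8.2 applies the 6.5 imputation to them in ITT and mITT.

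A reader might also set the planned LACTIN-V recurrence of 15% (30% halved, SAP 5) against 61% colonization and say that the tables would report one for the other. That contrast needs the literal reading that the shells rule out. It also compares a cumulative 12-week planning rate, which one visit would not reach, with a 4-week estimate from at most 24 × 3/4 = 18 women on a once-weekly maintenance schedule.

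**Conclusion.** The by-visit definition in SAP 8.2 is wrong as written and should be corrected. It covers the by-visit colonization tables, their menses and intercourse breakdowns, and the by-visit chi-square tests. It does not reach Tables 21 and 22, the primary endpoint or the sample size.

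The numerator error would probably be caught in programming; the denominator is the open choice. Its illustrative effect on one arm is 0 to about 6 percentage points at 61% colonization. That rests on an assumed 0% to 10% of attendees having no result, with absence unrelated to colonization status. No effect on the comparison between arms has been shown; it would depend on missingness by arm and on colonization in the placebo arm, and the documents give neither. This is a minor but definite correction.

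**What to change.** Replace the sentence in SAP 8.2 so that, for every by-visit colonization summary:

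- the numerator is subjects with successful colonization under 3.3.3 at that visit;
- the denominator is subjects in the population and subgroup with colonization data, and the subgroup variable where one applies, available at that visit;
- an indeterminate qPCR result counts as available data and as not colonized, in line with 3.3.3. A denominator worded as evaluable qPCR should be avoided, because it could drop these women.

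In the same edit, bring the by-visit BV recurrence text in 8.2 into line with the Table 13 note (BV diagnosis data available), and give the notes to Tables 77 and 81, and the tables that share their format, the data-available denominator. The reference to BV recurrence in the time-to-colonization paragraph can be corrected at the same time.

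The cost is a few lines of text. No new data, visits or sample size change are needed. The edit is best made before unblinding, so that the denominator is fixed without knowledge of the results.

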3.2.3 Secondary Efficacy Outcome Measures

Secondary Outcome Measure 1

The proportion of participants experiencing successful colonization with *L. crispatus* CTV-05 following dose of study product through Visit 4 (Week 12, Day 84) in the LACTIN-V arm, overall and by occurrence of menses and intercourse

Secondary Outcome Measure 2

The proportion of participants experiencing successful colonization with *L. crispatus* CTV-05 following dose of study product at Visit 7 (Week 24, Day 168) in the LACTIN-V arm, overall and by occurrence of menses and intercourse

Secondary Outcome Measure 3

Tolerability of LACTIN-V and the applicator will be measured by:

1. The proportion of participants who discontinue study product early in each study arm due to adverse events

Acceptability of LACTIN-V and the applicator will be measured by:

1. The proportion of participants who are compliant with the complete dose regimen in each study arm as assessed by participant reporting and applicator staining
2. Self-administered questionnaires about acceptability of the study product in each study arm

Secondary Outcome Measure 4

The proportion of participants with a positive BV diagnosis in each study arm by Visit 7 (Week 24, Day 168)

Exploratory Outcome Measure

The statistical parameterizations of the exploratory objective will include, but are not limited to, the following:

1. The number of BV recurrences per 12 weeks of follow-up
2. The probability of BV recurrence during the 12 weeks of follow-up

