Follow-up visits are scheduled 4, 8, 12 and 24 weeks after enrollment. A memory aid to gauge symptoms and AEs will be reviewed, a questionnaire to collect clinical, including AEs, data will be administered and a pelvic exam will be performed to detect genital tract AEs. Vaginal swabs for wet mount evaluation (Amsel criteria) and Gram stain evaluation (Nugent score) will be collected. A vaginal swab for *L. crispatus* (including CTV-05) identification will be collected. Vaginal applicators will be collected at Visits 2, 3, and 4 and stained with Trypan Blue upon return to the site as a proxy for product use. Telephone interviews will be scheduled between the 12 and 24 week visits, at 16 and 20 weeks after enrollment.

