11.3 Study Hypotheses

There are two planned formal tests of hypotheses which compare LACTIN-V to placebo, with respect to the primary safety and efficacy outcome measures. The first hypothesis test compares the proportion of participants in each study arm who experience AEs or SAEs considered product related following the first dose of study product through Visit 7 (Week 24, Day 168). The second hypothesis test compares the proportion of participants in each study arm who experience BV recurrence by Visit 4 (Week 12, Day 84).

The null hypothesis for each comparison is that there is no difference in proportions between study arms, with a two-sided alternative. The test for the primary safety hypothesis will be conducted using the Fisher's exact test at the 5% two-sided level of significance without adjustment for multiplicity. The test for the primary efficacy hypothesis will be conducted using the Pearson's chi-square test at the 5% two-sided level of significance without adjustment for multiplicity. No adjustments for multiplicity will be used as this is a Phase II-b trial which will provide screening evidence about safety and efficacy for a subsequent Phase III trial.

The primary safety hypothesis will be tested in the safety data analysis population. The primary efficacy analysis will be conducted in the Complete Case analysis population, and repeated as a secondary analysis in the modified intent-to-treat and Per Protocol analysis populations. See Section 11.6.2 for definitions of and rationales for use of the analysis populations.

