11.4 Sample Size Considerations

Sample size calculations are based on the assumption of detecting a 50% reduction in the cumulative proportion of participants who experience BV recurrence by 12 weeks post-administration of study product among participants receiving LACTIN-V compared to those receiving placebo in a complete case analysis at the 0.05 significance level. The proportion of participants among controls who will experience BV recurrence at 12 weeks is assumed to be 30%. We assume a LACTIN-V to placebo allocation ratio of 2:1 and 10% of subjects drop-out from the Complete Case population. Given logistical and feasibility constraints on the sample size and that this is a Phase II-b trial which will provide screening evidence about safety and efficacy for a subsequent Phase III trial, this trial is powered at the 70% level. Given the assumptions above, a sample size of 228 participants is required to detect a 50% reduction in the cumulative proportion of participants experiencing recurrence in the Complete Case population with 70% power using the Pearson Chi-Square test.

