	Vaginal swab for qPCR (L. crispatus identification)		X	X	X	X			X	X	X	X
Other Procedures	Acceptability questionnaire	X				X					X	X
	Staining of used applicators			X*								
	Telephone interview						X	X				

(X) if indicated
X* per site discretion

**APPENDIX B
DIVISION OF AIDS TABLE FOR GRADING THE SEVERITY OF
ADULT AND PEDIATRIC ADVERSE EVENTS PUBLISH DATE: DECEMBER 2004**

**Addendum 1
Female Genital Grading Table for Use in Microbicide Studies**

INDIVIDUAL SIGNS/SYMPTOMS				
PARAMETER	GRADE 0 NORMAL	GRADE 1 MILD	GRADE 2 MODERATE	GRADE 3 SEVERE
GENERAL				
Odor	No complaint	Mild-moderate unpleasant odor	Severe unpleasant odor	NA
PAIN AND TENDERNESS (Specify Area: Vulvar/Perineum, Vagina, Cervix (including cervical motion tenderness), Uterus, Adnexae, Pelvic/Lower Abdominal, or Ovulatory)				
*Note – if both pain and tenderness are present, only report the one with the most severe grade				
Pain* ¹	None	Pain causing no or minimal interference with usual social & functional activities	Pain causing greater than minimal interference with usual social & functional activities or the need for non-narcotic medication	Pain causing inability to perform usual social & functional activities or the need for narcotic medication OR hospitalization (other than emergency room visit) indicated
Tenderness* ¹	None	Mild tenderness	Moderate tenderness	Severe tenderness
Dyspareunia (pain with sexual activity)	None	Pain causing no or minimal interference with sexual function	Pain causing greater than minimal interference with sexual function	NA
Dysmenorrhea/cramping with menses	None	Pain causing no or minimal interference with usual social & functional activities	Pain causing greater than minimal interference with usual social & functional activities or the need for non-narcotic medication	Pain causing inability to perform usual social or functional activities or the need for narcotic medication

¹ If pain or tenderness is included in the grading of another category (e.g., PID), it should not be graded again in the pain or tenderness category

NOTE: For protocols utilizing this Addendum, when the same parameter appears in both this Female Genital Grading Table and the main DAIDS AE Grading Table, use the grading scheme in this table.

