3.2.3. Secondary Outcome Measures

1. The proportion of subjects experiencing successful colonization with *L. crispatus* CTV-05 following dose of study product through Visit 4 (Week 12, Day 84) in the LACTIN-V arm, overall and by occurrence of menses and intercourse.
2. (*Acceptability of LACTIN-V and the applicator*): The proportion of subjects who are compliant with the complete dose regimen in each study arm as assessed by subject reporting and applicator staining.
3. (*Tolerability of LACTIN-V and the applicator*): The proportion of subjects who discontinue study product early in each study arm due to adverse events.

-
4. (*Acceptability of LACTIN-V and the applicator*): Self-administered questionnaires about acceptability of the study product in each study arm.
 5. The proportion of subjects experiencing successful colonization with *L. crispatus* CTV-05 following dose of study product at Visit 7 (Week 24, Day 168) in the LACTIN-V arm, overall and by occurrence of menses and intercourse.
 6. The proportion of subjects with a positive BV diagnosis in each study arm by Visit 7 (Week 24, Day 168).

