3.3.5. Treatment Compliance

All subjects are to receive a total of 25 doses of study product. The first dose is administered in clinic and the remaining doses will be administered by the subject at home. A subject is compliant with the assigned study product if she takes at least 75% of the scheduled doses prior to the first diagnosis of BV or through Visit 4 (Week 12, Day 84), whichever occurs first. Compliance will be assessed by applicator staining of the returned kit. If a kit is not returned, compliance will be assessed by the subject's self-report (e.g. via the memory aid). If an incomplete kit is returned or staining results are indeterminate, the subject's self-report will be used in conjunction with the count of stained applicators to determine subject compliance.

Compliance is assessed on a weekly basis, so for subjects who are not compliant per the definition above, the time (week) at which the subject became non-compliant will be determined. The time of non-compliance will be defined as the first week at which the cumulative proportion of doses taken drops below 75% of the scheduled doses up to that week.

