As an additional analysis of the colonization analyses, the median time to colonization (from randomization) will be estimated by treatment group using Kaplan-Meier estimates ([Table 54](#)). In addition, the median 95% confidence interval, minimum, first quartile, third quartile, and maximum Kaplan-Meier estimates of time to BV recurrence will be presented. For subjects who experience colonization by Visit 4 (Week 12), the time of colonization will be defined as the midpoint between the earliest time point of colonization (post-baseline) and the previous observed time point. For subjects without colonization at or before Visit 4, the colonization endpoint will be coded as censored, with time to colonization defined as the elapsed time from the first dose of study product, to the Visit 4 time point, or to the first occurrence of loss to follow-up or the time-point at which the subject became ineligible for the particular analysis population. Time to colonization by Visit 7 (Week 24) will be defined similarly. Kaplan-Meier curves for colonization will also be generated ([Figure 4](#) and [Figure 5](#)).

[Table 55](#) will present the proportion of subjects who were compliant (See Section 3.3.5) with the dose regimen through their first BV recurrence or through Visit 4 (Week 12) (and 95% Wilson confidence interval) in each treatment group with difference in compliance proportions between treatment groups (and 95% Wilson confidence interval). The summaries will be presented in the ITT, mITT, and CC populations. The p-value from the Chi-Square test will also be presented. [Table 56](#), [Table 57](#), [Table 58](#), [Table 59](#), [Table 60](#), [Table 61](#), and [Table 62](#) will present summaries of product administration via subject report, returned applicators, and staining for each week. Summaries will be presented by clinical site and treatment group. [Listing 7](#) and [Listing 8](#) will present individual dosing data.

The responses to the acceptability questionnaire at screening and at Visit 4 (Week 12) will be summarized by treatment group. For categorical responses, the proportion of subjects with the particular response and its associated 95% Wilson confidence interval will be used ([Table 63](#) and [Table 64](#)). For continuous or discrete responses, the mean, standard deviation, median, and range of responses will be used ([Table 65](#) and [Table 66](#)).

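### The between-arm compliance test (SAP Table 55) stops counting doses at a woman's first BV recurrence, although both documents define the outcome on the complete dose regimen

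*SAP*

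**What the plan says.** The outcome is worded the same way in both documents. Protocol 3.2.3 has "The proportion of participants who are compliant with the complete dose regimen in each study arm", and SAP 3.2.3 has "The proportion of subjects who are compliant with the complete dose regimen in each study arm". SAP 3.3.5 puts the regimen at 25 doses. Protocol 11.6.4.2, which plans the between-arm test, gives no threshold and no cut-off at recurrence.

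The scoring rule is different. Under SAP 3.3.5 a woman is compliant if she "takes at least 75% of the scheduled doses prior to the first diagnosis of BV or through Visit 4", whichever comes first. SAP 8.2 applies that rule to Table 55, which counts women compliant "with the dose regimen through their first BV recurrence or through Visit 4 (Week 12"), with a chi-square p-value. In the protocol the same 75% rule stands in 11.6.2, directly after the Per-Protocol definition. SAP Section 13, which lists departures from the protocol, does not mention its use for this outcome.

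Dosing does not end at recurrence. Protocol 7.3 has re-treated women skip product during MetroGel and then resume twice weekly. Women with asymptomatic BV are not re-treated, and nothing in the section stops their product.

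On measurement, Protocol 4.0 says "Vaginal applicators will be collected at Visits 2, 3, and 4 and stained with Trypan Blue upon return to the site". The schedule in Protocol Appendix A carries the footnote "X* per site discretion" against staining.

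**The concern.** For Per Protocol membership, counting doses only up to the first event is reasonable, because later doses cannot affect that event. Acceptability is a different question: did women use the product through the course? A woman who takes all 11 doses due by Day 28, is BV-positive at Visit 2 and never opens another applicator has used 11/25 = 44% of the regimen, yet Table 55 counts her as compliant.

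The efficacy outcome sets the length of the window, and the design expects that outcome to be twice as common on placebo. The arms are therefore compared over windows of different average length. Table 55 is the only formal between-arm test of compliance, and it is blind to the period after recurrence, when a woman might well lose faith in the product.

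**Working it through.** **Plan's own figure.** The documents state no figure for compliance, so the sample size is checked only to confirm the recurrence rates used below. Protocol 11.4 assumes 30% vs 15%, 2:1 allocation, 70% power and 10% drop-out, "in a complete case analysis at the 0.05 significance level". Protocol 11.3 tests "using the Pearson's chi-square test at the 5% two-sided level of significance without adjustment for multiplicity".

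- Pooled rate = (0.30 + 2×0.15)/3 = 0.20.
- Placebo n = [1.96×√(0.20×0.80×1.5) + 0.524×√(0.21 + 0.1275/2)]² / 0.15² = 67.7, so 68.
- Total = 3×68 = 204, and 204/0.90 = 227. The plan states 228 (76 placebo, 152 LACTIN-V), so it reproduces to within rounding.

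**Dose windows** (Protocol 6.2: five doses in Week 1, then two a week in Weeks 2 to 11; visits on target days):

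| First recurrence | Doses scheduled | Needed for 75% |
|---|---|---|
| Visit 2 | 5 + 2×3 = 11 | 9 |
| Visit 3 | 5 + 2×7 = 19 | 15 |
| Visit 4 or none | 25 | 19 |

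**Who is truncated.** Only recurrences at Visits 2 and 3 shorten the window. If recurrences split evenly over Visits 2 to 4 (assumed), that is 30%×2/3 = 20% of placebo women and 15%×2/3 = 10% of LACTIN-V women, or about 15 women in each arm (76×0.20 = 152×0.10 = 15.2).

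**Stopping after recurrence.** Simulation with even timing, 2% of women stopping per week after Week 1, and 95% of doses taken while on product. All the adherence inputs are assumptions.

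| Recurrers who then stop | Table 55: placebo / LACTIN-V | All 25 doses: placebo / LACTIN-V | Difference on all 25 doses (LACTIN-V minus placebo) |
|---|---|---|---|
| none | 86.7% / 86.2% | 85.6% / 85.5% | about 0 |
| half | 86.7% / 86.2% | 78.8% / 82.3% | 3.5 points |
| all | 86.7% / 86.2% | 71.7% / 78.7% | 7.0 points |

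Table 55 does not move while the full-regimen difference grows from 0 to 7 points.

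**Effect of timing.** A simpler model assumes 85% compliant up to recurrence in both arms, and counts every woman who stops after Visit 2 or 3 as non-compliant on the full regimen.

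- Even timing, all stop: 0.85×(1 − 0.20) = 68.0% vs 0.85×(1 − 0.10) = 76.5%, a gap of 8.5 points.
- Recurrences split 1/2, 1/3, 1/6 over Visits 2, 3 and 4: 0.85×(1 − 0.25) = 63.8% vs 0.85×(1 − 0.125) = 74.4%, a gap of 10.6 points.
- Table 55 shows 0 in both cases.

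**Waning adherence with no effect of recurrence.** Per-dose probability is 0.97 in Week 1, then falls linearly from 0.95 to 0.50 by Week 11, identically in both arms. The chance of meeting 75% is 0.968, 0.850 and 0.680 for the 11-, 19- and 25-dose windows.

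- Placebo: 0.10×0.968 + 0.10×0.850 + 0.80×0.680 = 72.6%.
- LACTIN-V: 0.05×0.968 + 0.05×0.850 + 0.90×0.680 = 70.3%.
- Table 55 shows −2.3 points (LACTIN-V minus placebo) where the true difference is 0. If the last-week probability is 0.90, it shows +0.1.

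**The case against.** **Protocol against SAP.** A reader might infer that the SAP departed from the protocol. That is too strong. The truncated 75% rule is the only numerical definition of compliance in the protocol, and the SAP reused it. The mismatch between outcome wording and scoring rule runs through both documents. It still needs resolving, because the protocol sets the rule beside the Per-Protocol definition and does not tie it to this outcome.

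**An easier window for placebo.** A reader might also infer that the shorter window flatters placebo. Not in general: 9/11, 15/19 and 19/25 are 82%, 79% and 76%, so rounding makes the short window stricter. At a constant 0.80 per dose the chances of passing are 0.62, 0.67 and 0.78. The short window is easier only if adherence wanes or women stop.

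**Other outputs.** Tables 56 to 62 show dosing week by week with no stop at recurrence, including one table per arm. Tables 43 to 45 classify compliance from the start of treatment to each visit, though only for women with colonization data, and their cross-reference back to 3.3.5 leaves the window unclear. Post-recurrence dosing is therefore not invisible. None of these outputs tests compliance between arms.

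**Power.** With 76 and 152 women, the test would have about 10% power for 78.8% vs 82.3% and about 22% for 71.7% vs 78.7%. The correction gives the right estimand; the test would still usually miss such a gap.

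**Staining.** One might infer that some sites do not stain. The evidence is one footnote to a single entry in a table flattened by text extraction, against body text that says applicators are stained. It may concern timing. It supports only a request to reconcile the passages.

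**Conclusion.** The point holds. A named secondary outcome is defined on the complete regimen and scored on a window that the efficacy outcome cuts short, more often on placebo under the design's own rates.

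The 20% vs 10% split rests on even timing over Visits 2 to 4. The size rests on adherence rates that the documents do not give: about 1 point if nobody stops after recurrence, a hidden arm difference of about 7 points if all recurrers stop (about 11 with earlier recurrences), or a spurious difference of up to about 2 points under waning alone. An unconditional claim that Table 55 overstates compliance by many points would not be supported: in the simulation, overstatement of about 4 to 15 points needs half to all recurrers to stop.

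The primary efficacy and safety analyses are untouched. The change is worth making because it is cheap and aligns the only formal compliance test with the stated outcome.

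**What to change.** In Table 55, score every woman on at least 75% of the 25 doses scheduled through Week 11, whatever her BV status, leaving out of the denominator any doses the protocol directed her to skip during MetroGel re-treatment. Keep the truncated rule for Per Protocol membership and, if wanted, as a supportive row. State in SAP 3.3.5 which definition serves which purpose, and list the change in SAP Section 13.

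The cost is SAP wording and one derived variable; the dosing data are already planned for Listing 7. The downside is that reported compliance may be lower.

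Separately, reconcile the Appendix A staining footnote (the asterisk also appears in SAP Table 2) with Protocol 4.0, 6.3 and 7.3 to 7.5. This touches the protocol as well as the SAP, and cannot recover any applicators already discarded unstained.
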